3 OBJECTIVES AND ENDPOINTS

OBJECTIVES	ENDPOINTS	JUSTIFICATION FOR ENDPOINTS	PUTATIVE MECHANISMS OF ACTION
Primary			
To examine the efficacy of CCT in reducing depressive and anxiety symptoms and improve cognitive control.	Depressive symptoms and cognitive control behavioral performance after the intervention.	We anticipate that CCT will result in increased cognitive control capacity, which will also relate to reductions in depressive symptoms.	Enhanced cognitive control ability (as trained with CCT) will improve the ability to regulate symptoms, thus lowering symptoms and reducing risk of developing full disorder.
Secondary*			
To examine the durability of change in depressive symptoms and cognitive control 3-months after the CCT intervention.	Depressive symptoms and cognitive control capacity 3-months post-intervention.	We anticipate that depressive symptoms will be reduced, and cognitive control enhanced, to a greater extent 3-months post-intervention as compared to immediately post-intervention.	Changes in cognitive control that may also support a reduction in depressive symptoms may have solidified over 3-months and therefore become detectable in self-report and clinician-administered assessments.
Feasibility/Acceptability and Experimental Outcomes			
1) To assess whether participants engage in the intervention as instructed.	1) Game-play metrics provided by Akili software; 2) ESS scores from	1) We anticipate that participants will play the game as instructed, 2) that they will have	Prior studies of EndeavorRx have demonstrated the feasibility and

OBJECTIVES	ENDPOINTS	JUSTIFICATION FOR ENDPOINTS	PUTATIVE MECHANISMS OF ACTION
2) To assess whether participants enjoy engaging in the intervention. 3) To examine whether the effects of CBT in the Parent study have been maintained at a 2-year follow-up.	each post-intervention assessment; 3) Depressive symptoms at Assessment #1 of current study	favorable emotions associated with game play and, 3) that depressive symptoms will still be reduced from the original baseline assessment, but that they will be greater than they were immediately after intervention in the Parent study.	acceptability of the intervention. Also, that treatment for anxiety disorders in the Parent study should also reduce co-morbid depressive symptoms, and that this reduction should be maintained over time.

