5 STUDY POPULATION

5.1 INCLUSION CRITERIA

In order to be eligible to participate in this study, an individual must meet the following criteria:

1. Parent or guardian willing to give informed consent, and children willing to give informed assent to participate in the study.
2. Males and females (age 9 – 17.99)
3. Participant is willing to engage in a technology-based intervention (technology will be provided to participants who live in the state of Michigan, if not already accessible to participant).
4. Self-reported depressive symptoms (CDI score between 3-19 at Assessment 1)
5. Participants will be required to maintain a stable dose of medications for 4 weeks prior to the first assessment and stable medication throughout the intervention period. Participants may change medication after completion of the post-intervention assessment (i.e. in between the post-intervention assessment and follow-up assessment).

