5.2 EXCLUSION CRITERIA

An individual who meets any of the following criteria will be excluded from participation in this study:

An individual who meets the following criteria will be excluded from participation in this study:

1. Color blindness
2. Unable to play the video game for any reason
3. K-SADS diagnosis of clinical depression, psychosis, or Autism Spectrum Disorder
4. Has enrolled in new psychotherapy (for the treatment of a mood or anxiety disorder) or had changes to their psychotherapy in the 4-weeks prior to study enrollment
5. Endorses items #1, #2, #3, #4, #5, #6 on the C-SSRS Screener (Past-Month); i.e., has present suicidal intention/behavior.
6. Has had any changes to their medication in the 4-weeks prior to study enrollment

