5.5 STRATEGIES FOR RECRUITMENT AND RETENTION

Recruitment will be mostly from participants who had already enrolled in the Parent study and who, at the time of enrollment in the parent study, had consented to be re-contacted for research purposes. All participants will be contacted via phone call or email and asked if they are interested in hearing about another research study involving a preventative intervention. If they are, we will conduct our phone screen to determine initial eligibility and whether they should be scheduled for a consent visit. After the original contact, we may also reach out to parents via text message (using a prepared and approved message template) to direct their attention to their voicemail or email, and request to schedule a phone screen. Parents of potential participants will be contacted from the sample of eligible participants of the Parent study until target enrollment of the current protocol is reached. If it is decided to recruit from outside of the Parent study, those new participants will be not be contacted via text message to complete the phone screen, as we will not have access to their contact information at that time. Only participants from the Parent study (who had consented to be re-contacted originally) will be contacted via text message).

Participants from the Parent study were initially recruited to the Parent study from outpatient psychiatry programs at the University of Michigan Health System, from multi-media advertisements (UMClinicalStudies.org, passive advertisements on social media sites and Craigslist Ann Arbor, Google Adword campaigns, print and electronic media, radio ads and flyers) and by referral from community clinicians. Participants from the Parent study can be enrolled in the current protocol if they previously endorsed elevated depressive symptoms during the Parent study and do not possess any of the exclusionary criteria. Initial screening will occur in a telephone interview. Participants can enroll in the study from anywhere in the United States, as all aspects of the study protocol will be completed remotely. Based on the demographic characteristics of the sample with elevated depressive symptoms (CDI T-scores > 50) from in the Parent study, we anticipate that the sample of the current protocol will be primarily composed of youth that identify as female (90%) and are Caucasian (75%).

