9 STATISTICAL CONSIDERATIONS

9.1 STATISTICAL HYPOTHESES

Primary Endpoint:

We hypothesize that CCT will increase cognitive control capacity (Millisecond battery composite score and individual cognitive test scores) and reduce depressive symptoms (CDI and CDRS-R scores) over the 4 week period of the intervention. Specifically, we hypothesize that CCT will improve cognitive control which will in turn improve depressive symptoms as a consequence of enhanced emotional regulation. Alternatively, our null hypothesis is that there will be no difference in cognitive control capacity or depressive symptoms immediately post-intervention as compared to pre-intervention.

Secondary Endpoint*:

We hypothesize that CCT will further increase cognitive control capacity (measured by Millisecond battery composite score and individual cognitive test scores) and reduce depressive symptoms (as measured by CDI and CDRS-R) further 3-months post-intervention than immediately after the intervention. The null hypothesis is that there is no difference in cognitive control capacity or depressive symptoms from immediately post-intervention to 3-months after the intervention.

*Secondary endpoint was optional to participants and then discontinued after protocol version 2.1 (02 April 2024).

Feasibility/Acceptability and Experimental Endpoints:

1. We hypothesize that the majority of participants will complete the intervention with at least 80% compliance.
2. We hypothesize that participants will have favorable emotions associated with game play.
3. We hypothesize that depressive symptoms will be reduced from the baseline assessment of the Parent study but that they will be slightly elevated from the post-intervention assessment in the Parent study.

The statistical tests used to test these hypotheses will be outlined later in this protocol and registered with clinicaltrials.gov.

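### Hypothesis 3 judges 2-year maintenance of CBT benefit by a one-group fall from Parent-study baseline; selection can produce such a fall, and no CBT-versus-RMT analysis is tied to it

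*Combined protocol and SAP*

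**What the plan says.** - **Objective.** Section 3 (also the synopsis and the fourth aim in 4.2) sets the question: "To examine whether the effects of CBT in the Parent study have been maintained at a 2-year follow-up". The endpoint is depressive symptoms at Assessment 1. Section 4.2 limits the aim to where it is applicable.
- **Hypothesis.** Section 9.1, third item under the feasibility and experimental endpoints: "We hypothesize that depressive symptoms will be reduced from the baseline assessment of the Parent study". It adds that symptoms should be slightly higher than at the end of Parent-study treatment. Neither half names a treatment arm, although section 4.1 says that the Parent study randomised 148 youths 2:1 to CBT or RMT.
- **Entry on an earlier score.** Section 5.5: "Participants from the Parent study can be enrolled in the current protocol if they previously endorsed elevated depressive symptoms during the Parent study". The Parent-study visit is not stated. The same section, when forecasting demographics, describes the group as having "elevated depressive symptoms (CDI T-scores > 50".
- **Limits at the endpoint visit.** Section 5.1 requires "Self-reported depressive symptoms (CDI score between 3-19 at Assessment 1"; section 5.2 excludes a "K-SADS diagnosis of clinical depression, psychosis, or Autism Spectrum Disorder".
- **Analysis.** Section 9.1 promises: "The statistical tests used to test these hypotheses will be outlined later in this protocol and registered with clinicaltrials.gov". Sections 9.4.1 to 9.4.9 give no test for this hypothesis and mention neither CBT nor RMT. Section 4.1 has one sentence on multilevel models comparing former CBT and RMT recipients. It mentions neither Parent-study baseline nor the 2-year question.

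**The concern.** Whether a CBT effect has lasted is a comparative question: are former CBT children still better off than they would have been without CBT? A fall from each child's own Parent-study baseline does not answer it. RMT children count towards the fall as much as CBT children do, and natural change is included.

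Selection adds to this. A child invited because of a high earlier score will, on average, score closer to the mean two years later. A child who has relapsed above CDI 19 or into clinical depression cannot enter at all. Both mechanisms push the measured change downwards.

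The risk is in the conclusion drawn. The rationale in section 3 already expects that "this reduction should be maintained over time", so an observed fall invites the reading that CBT was durable when selection alone could explain it.

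**Working it through.** **No figure to reproduce.** The plan gives no sample size, effect size or test for this hypothesis. Section 9.2 states 32 participants for 80% power without an effect size, SD or correlation. The size of the artefact must therefore rest on assumptions.

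**Assumptions (not in the documents).** Mid case: Parent-study CDI mean 12, SD 7; correlation 0.5 between baseline and the 2-year visit, 0.6 between adjacent visits; mean fall of 2 points by the end of Parent treatment; 2-year mean back at Parent baseline, so nothing is maintained; elevated means raw CDI above 7, standing in for T > 50. From the plan: CDI 3-19 at Assessment 1, n = 30, two-sided 0.05. Scores were drawn as trivariate normal, rounded and limited to 0-54. Only significant falls are counted, so the nominal rate is 2.5%.

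**Step 1: prior elevation alone, by formula.** Expected fall = SD × (1 − r) × φ(c) / (1 − Φ(c)). With rounded scores, c = (7.5 − 12)/7 = −0.643, φ(c) = 0.324 and 1 − Φ(c) = 0.740. The fall is 7 × 0.5 × 0.324/0.740 = 1.5 points.

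**Step 2: add the 3-19 window, by simulation.**

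| Elevation judged at | Nothing maintained: mean fall | Significant fall | Same, if untreated symptoms rise 2 points |
|---|---|---|---|
| Parent baseline | 2.4 points | 65% | 23% |
| Either Parent visit | 1.4 points | 24% | 4% |
| Parent post-treatment only | 1.1 points | 15% | 2% |
| No prior-elevation rule, window only | 0.4 points | 5% | not needed |

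Check on the first row: the simulated SD of change is about 5.5, so the expected t is 2.4/(5.5/√30) = 2.4/1.00 = 2.4, against a critical value of 2.05. A rate near 65% follows. With an untreated rise of 3 points, the first two rows fall to 9% and 1%.

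**Step 3: range.** With no untreated rise, the grid was mean 10-14, SD 7-8, correlation 0.3-0.7, post-treatment fall 0-4 and raw cut 5-9. The false-fall rate is 23-99% for baseline elevation, 5-71% for either visit, 4-53% for post-treatment only and 2-17% for the window alone.

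**Step 4: the arm contrast.** Assume post-treatment falls of 4 points (CBT) and 1 point (RMT), with nothing maintained at two years. The CBT-minus-RMT difference in change from Parent baseline is then −0.03 to +0.04 points if elevation was judged at baseline. Under either-visit selection it leans towards CBT by 0.2 to 0.8 points (about 0.4 in the mid case), because fewer CBT children qualify on the post-treatment score alone. With 20 CBT and 10 RMT, it falsely favours CBT in 2.0-2.9% of studies (baseline) or 3.1-5.5% (either visit). On the same simulated children, the one-group test gives 23-99% and 9-65%.

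**Step 5: precision of the contrast.** Half-width of the 95% CI = t(28) × √(1/20 + 1/10) = 2.048 × 0.387 = 0.79 SD. On simulated change SDs of 4.5 to 7.8, that is about 3.6 to 6.2 CDI points. Power of 80% needs d = 1.12. At 12 v 6 the half-width is 2.120 × √(1/12 + 1/6) = 1.06 SD. The 3-19 window also shrinks a true 3-point difference to 1.2-2.3 points under baseline elevation.

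**The case against.** **Untreated symptoms may rise.** Section 2.2.1 expects depression to emerge around puberty, notes especially high risk in anxious youth and reports rising rates. An upward drift offsets regression to the mean, as the last column of the table shows. This stands. A reader might infer that a false fall is likely; the documents support only that selection can produce one.

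**The selection visit is open.** Section 5.5 does not say when elevation was judged, T > 50 appears only in a demographic forecast, and prior elevation is not among the criteria in 5.1 and 5.2. This also stands, and it is why no single figure can be given. It does not make the one-group comparison a test of CBT.

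**Section 4.1 already compares CBT with RMT.** That sentence follows the pre/post-CCT comparison, covers cognitive control as well as symptoms, and may concern response to CCT by former arm. It cannot be counted on to cover the 2-year question.

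**No rule declares CBT durable.** Correct: the plan has no such decision rule, and hypothesis 3 also predicts some loss since post-treatment. That second half is one-group too, so it cannot separate CBT benefit from selection.

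**The contrast is weak.** True. It is imprecise, and because return and eligibility come after randomisation, it is not fully protected. That argues for estimation, or for no conclusion at all, rather than for the one-group reading.

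**Conclusion.** The point holds in limited form. The comparison in hypothesis 3 cannot support a statement that CBT effects were maintained, because it names no arm and because selection at entry and at the endpoint visit can produce the fall it looks for. Section 9.4 supplies no analysis that would correct this.

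In the assumed mid case, the false-fall rate runs from 65% down to 2%, depending on the selection visit and on whether untreated symptoms stay level or rise 2 points. The documents do not settle either matter. A reader might go further and infer that the trial will probably report a false CBT benefit, or that it is committed to doing so. Neither follows.

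Severity is minor. This is the third experimental objective of a non-randomised pilot, pursued only if applicable, and the point does not touch the primary analysis. It is a cheap improvement.

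**What to change.** In 9.1 and 9.4:

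1. State that the one-group changes from Parent baseline and from Parent post-treatment are descriptive, are limited to Parent-study participants (community recruits have no Parent-study scores), and will not be interpreted as maintained CBT benefit.
2. Specify, as the analysis for hypothesis 3, the CBT-minus-RMT difference in change from Parent baseline to Assessment 1, reported as an estimate with a 95% CI and no significance claim. Write it out in full rather than refer to section 4.1.
3. Add a sensitivity analysis restricted to children who were elevated at the Parent pre-randomisation baseline, since selection at either visit tilts the contrast towards CBT.
4. If too few children return for the contrast to be feasible, report Assessment 1 scores descriptively and draw no conclusion on durability.

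Adding back children who screened out is not advised. Section 2.3.1 says that screening forms of those who do not qualify are destroyed, apart from information that cannot be linked to the child and certain records of children who may soon become eligible.

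The cost is a few sentences, with no new data and no change to recruitment or consent. The downside is an imprecise estimate that is open to differential return by arm; the text should say so.

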9.2 SAMPLE SIZE DETERMINATION

Sample size was determined based on results from a power analysis and feasibility of participant recruitment. A sample size of 32 participants would yield 80% power for the planned analyses in the current study, but 30 participants is a more achievable initial target for recruitment. Though there is minimal data

to generate hypothesized effect sizes, the proposed study will allow for generations of effect sizes to be used in future, larger studies.

9.3 POPULATIONS FOR ANALYSES

Complete-Case Analysis Population: This population will consist of enrolled participants without missing data on variables of interest from Assessment #2.

Per-Protocol Analysis Dataset: This population will consist of participants who complete all four weeks of the intervention (with at least 80% compliance to the guidelines of 25 minutes/day for 5 days a week across the 4 weeks. Compliance of 80% can be achieved by completing at least 20 minutes of gameplay on 80% of the days that they could play the game in the 4 week period, if assuming a 5-day week. For instance, assuming that a participant would complete at least 20 minutes of gameplay for 20 days during the 4 week period, a participant with 80% compliance would engage in at least 20 minutes of gameplay for at least 16 days during this period. Compliance will be assessed using gameplay metrics provided by Akili that are automatically measured when the game is played on a participant's device.

9.4 STATISTICAL ANALYSES

9.4.1 GENERAL APPROACH

Data will be analyzed using statistics software such as SPSS and R software. For descriptive statistics, means with standard deviation and range will be computed for continuous data (all behavioral data and some of the clinical data). In general, statistical significance is reported based on $p < 0.05$ two-tailed. Missing data from Assessment 3 (if applicable) will be handled using pairwise deletion. Missing data from Assessment 1 or 2 will be handled using listwise deletion.

9.4.2 ANALYSIS OF THE PRIMARY ENDPOINT(S)

We hypothesize that CCT will increase cognitive control capacity and reduce depressive symptoms. The hypothesis will be tested using paired samples (repeated measures) t -tests (pre vs. post) for each dependent variable (CDI score and Millisecond battery composite score). Both of these dependent variables are interval variables.

Standard deviations and effect sizes will be assessed for each of these analyses.

9.4.3 ANALYSIS OF THE SECONDARY ENDPOINT(S)*

We hypothesize that CCT will further increase cognitive control capacity (measured by Millisecond battery composite scores) and further reduce depressive symptoms (as measured by CDI and CDRS-R) 3-months post-intervention than immediately after the intervention. This hypothesis will be tested using repeated-measures ANOVAs, with three timepoints (pre-intervention, immediately post-intervention, and 3-months post intervention), on behavioral performance (cognitive control capacity) and depressive symptoms.

Standard deviations and effect sizes will be assessed for each of these analyses.

*Secondary endpoint was optional to participants and then discontinued after protocol version 2.1 (02 April 2024).

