4.2 SCIENTIFIC RATIONALE FOR STUDY DESIGN

We hypothesize that CCT will improve cognitive control capacity and thereby reduce depressive symptoms post-intervention and (if applicable) after a 3-month period post intervention. Therefore, we will enroll youth with subclinical depressive symptoms to complete the CCT intervention and measuring their cognitive control capacity and clinical symptomology after the intervention.

The aims of this project are to:

1. Examine whether CCT will reduce depressive and anxiety symptoms and improve cognitive control after the 4-week intervention.
2. If applicable, examine whether the effects of CCT change in a 3-month period after the CCT intervention.
3. Examine the feasibility and accessibility of the CCT intervention.
4. If applicable, examine whether the effects of cognitive behavioral therapy (CBT) in a previous intervention and protocol have been maintained at a 2-year follow-up.

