9.4.7 SUB-GROUP ANALYSES

The sample included in this pilot study will not be large enough to conduct subgroup analyses based on sex or race/ethnicity. However, if applicable, in the secondary endpoint models, age and sex may be included as covariates. The current analyses will assess the efficacy of the study intervention in youth only (ages 9-17).

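### The three-timepoint ANOVA in 9.4.3 does not test the post-to-3-month null stated in 9.1, so a pre-post change alone can make it significant (minor; only for Assessment 3 data collected before version 2.1)

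*Combined protocol and SAP*

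**What the plan says.** Section 9.1 gives the secondary null: "The null hypothesis is that there is no difference in cognitive control capacity or depressive symptoms from immediately post-intervention to 3-months after the intervention". Section 9.4.3 states the alternative with a direction. Cognitive control is to rise further, and depressive symptoms (CDI and CDRS-R) are to fall further, "3-months post-intervention than immediately after the intervention".

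The test follows in the same section: "This hypothesis will be tested using repeated-measures ANOVAs, with three timepoints (pre-intervention, immediately post-intervention, and 3-months post intervention". Section 9.4.3 adds that standard deviations and effect sizes will be assessed. It names no planned contrast, trend test or follow-up comparison. Section 4.1 mentions multilevel models of change over time, but it does not single out a post-to-3-month contrast either. Under Section 9.4.1, "statistical significance is reported based on $p < 0.05$ two-tailed".

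The synopsis and Section 3 phrase the secondary objective as durability of the change at 3 months. The synopsis, the schedule of activities and Sections 4.1, 4.4, 9.1 and 9.4.3 all record that Assessment 3 was removed at version 2.1 (02 April 2024). Several also say it had been optional. The analysis text is nevertheless kept conditionally. Aim 2 in Section 4.2 reads "If applicable, examine whether the effects of CCT change in a 3-month period after the CCT intervention", Section 9.4.1 has "Missing data from Assessment 3 (if applicable) will be handled using pairwise deletion", and Section 9.4.7 has "if applicable, in the secondary endpoint models, age and sex may be included as covariates".

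**The concern.** The null in 9.1 involves two visits, post and 3 months. The null of the ANOVA time effect involves three. Because the pre-intervention score is in the model, the pre-post change, which is the primary hypothesis, also drives the secondary test. If the training works in the short term and nothing happens afterwards, the 9.1 null is true and the ANOVA still tends to reject.

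The F test is also undirected. It cannot separate further gain, plain maintenance and a return to the starting level, and only the first of these is what 9.4.3 hypothesises. If the available 3-month data were analysed exactly as 9.4.3 is worded, a significant time effect could be taken as support for a hypothesis it does not address.

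**Working it through.** **The plan's own figure.** Section 9.2 says "A sample size of 32 participants would yield 80% power for the planned analyses in the current study", with 30 as the initial recruitment target. This cannot be reproduced, because no effect size, SD or within-child correlation is stated. Solving backwards for a two-sided paired t-test at 0.05, 32 children and 80% power imply dz = 0.511 (mean change divided by SD of change). A dz of 0.5 would need 34 children. A three-level ANOVA with f = 0.25 and correlation 0.5 would need 28. The value 0.51 is used below only as one reference point.

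**Inputs.** From the documents: alpha 0.05 two-sided (9.4.1), three timepoints (9.4.3), and the post-to-3-month null (9.1). Assumed: equal SDs of 1, a common correlation ρ = 0.5 between visits, and pre-post dz of 0.2, 0.3, 0.51 or 0.8. The number with Assessment 3 data is not given, so n = 10, 15, 20 and 30 are shown.

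**Formula.** Let δ be the mean pre-post change, so δ = dz × √(2(1−ρ)).

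- Maintenance (9.1 null true): means (0, −δ, −δ), sum of squares about their mean 2δ²/3.
- Full relapse: means (0, −δ, 0), sum of squares also 2δ²/3.

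The omnibus F has 2 and 2(n−1) degrees of freedom and noncentrality λ = n × (2δ²/3)/(1−ρ). Substituting δ² = 2(1−ρ)dz² gives λ = (4/3) × n × dz². The correlation cancels, and the two scenarios give the same rejection rate.

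**Worked cases.** For n = 20, dz = 0.3: λ = (4/3) × 20 × 0.09 = 2.4, critical F(2, 38) = 3.245, rejection 25%. For n = 30, dz = 0.511: λ = (4/3) × 30 × 0.2614 = 10.46, critical F(2, 58) = 3.156, rejection 81%.

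**Chance that the omnibus time effect is significant (same for maintenance and full relapse)**

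| pre-post dz | n = 10 | n = 15 | n = 20 | n = 30 |
|---|---|---|---|---|
| 0.2 | 9% | 11% | 13% | 18% |
| 0.3 | 13% | 19% | 25% | 36% |
| 0.51 | 32% | 48% | 62% | 81% |
| 0.8 | 67% | 87% | 95% | 99.6% |

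Simulation (10,000 trials per case) at n = 15, 20 and 30 with dz 0.3, 0.51 and 0.8 agrees to within about one percentage point. With no change at any visit the omnibus F rejects about 5%, so the excess comes from testing a different null and not from the method of calculation.

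**The direct contrast in the same simulations.** Under maintenance, the paired t-test of 3 months against post rejects about 5% two-sided, roughly half of that in the hypothesised direction. Under full relapse with n = 30 and dz = 0.51 it signals worsening about 77% of the time and further improvement about 0%. The ANOVA is significant 81% of the time in both scenarios and does not tell them apart.

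**The case against.** The strongest reply is that the endpoint has been retired. The visit was optional, it was removed so that effort could go to recruitment, and the documents neither give a number of completers nor commit to a confirmatory analysis of them. This stands as a limit on importance. It does not make the point moot, because the aim, the missing-data rule and the covariates remain where applicable, and 9.4.3 is the only test on paper for whatever 3-month data exist.

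The second reply is that nobody would interpret F without looking at the means. Sections 9.4.1, 9.4.3 and 9.4.8 call for means, SDs, effect sizes and listings by timepoint, so a relapse would be visible. That also stands. The text is under-specified. It does not commit the team to inferring direction from F, and a reader who concludes that every significant time effect would be reported as further improvement goes beyond the documents. What remains is that the comparison answering 9.1 is left to be chosen after the data are seen.

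Three stronger readings are tempting and should be resisted.

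- The relapse figures might be taken as false-positive rates. They are not: under full relapse post and 3 months differ, the 9.1 null is false, and rejecting it is correct. The fault would lie only in reading the rejection as further improvement or durability. Only the maintenance scenario inflates type I error.
- The larger entries in the table might suggest that the error is always many times nominal. At dz = 0.2 and n = 10 it is 9%, under twice 5%. The plan gives no basis for ruling out small effects or small numbers.
- The pairwise-deletion rule might be called incompatible with the ANOVA. A standard repeated-measures ANOVA does use only children with all three scores, but 9.4.1 is a general rule and is workable for two-visit comparisons, so it is not a separate defect.

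Finally, a post-to-3-month test alone would not settle durability, which is the objective in the synopsis and Section 3. That is right, and it shapes the fix.

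**Conclusion.** The point holds, at minor severity, for Assessment 3 data collected before version 2.1. The test named in 9.4.3 has a different null from the one in 9.1 and has no direction. When the 9.1 null is true, a pre-post change can make the test significant. The rate runs from about 9% (dz 0.2, n = 10) to 99.6% (dz 0.8, n = 30) against a nominal 5%.

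These figures rest on assumed effect sizes, an unknown number of children with 3-month data, and equal SDs and correlations across visits. Under that structure the size of the correlation does not matter. A significant time effect under relapse is not a type I error, but it supports neither further improvement nor durability.

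**What to change.** In 9.4.3, name the 3-month minus immediate-post contrast as the test of the 9.1 hypothesis, separately for CDI, CDRS-R and the Millisecond composite. It can be a paired t-test, or that contrast taken from the repeated-measures or mixed model, so the three-timepoint model need not be dropped. Report each contrast with its direction and 95% CI.

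For the durability objective, also report the 3-month minus pre difference with its 95% CI. State that a non-significant post-to-3-month contrast is not proof of maintenance. Label the omnibus time effect descriptive, and say that the section applies only to Assessment 3 data collected before version 2.1.

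The cost is a few sentences, with no new data or visits. The downside is that the direct contrast will often fail to reach significance where the omnibus test would have done so, and its interval will be wide if few children completed Assessment 3.
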